The prevalence of FA is estimated to be 25% in the population of urban adult women who have a BMI classification of overweight or obese. Using this prevalence along with a medium effect size, a statistical power analysis was performed for sample size estimation with G\*Power 3.1. The design is a stratified four-group design with a pre and post measurement. Stratification by obesity phenotype (positive or negative for FA) will occur first, followed by random assignment to one of four treatment groups [Information Control (dietary and physical activity instruction), MI alone(diet and physical activity instruction supported by MI), MI((diet and physical activity instruction supported by MI+P(Contrave)). Using an  $f = 0.25$ , an  $\alpha = .05$  and  $\text{power} = 0.95$ , the a priori F test, analysis of variance, omnibus, one-way model gives a projected sample size of 252. As a pilot study, this study is underpowered for statistical hypothesis testing, and analyses will focus on descriptive statistics, estimation of effect sizes, and hypothesis generation and a sample of 40 eligible patients will be enrolled (10 in each group). This meets the pilot study guideline of at least 10% of a fully powered trial and remains realistic in terms of time and cost (Hertzog, 2008) while allowing for 50% attrition. It is expected that 25% of the population will meet the criteria of FA and therefore will need to screen and consent a total of 160 participants to reach the 40 people positive for FA. No more than 160 subjects will be consented for the entire pilot study.

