#### Statistical Methods to Analyze Data

Missing data will be evaluated. For summated scales on which fewer than 20% of an individuals responses are missing, the individuals mean on the remaining items may be substituted, as appropriate. For analyses requiring complete data, imputation of missing values using the EM algorithm or multiple imputations will be considered, as appropriate. Scoring algorithms for each instrument will be used per the published use manual. Each statistical test will be conducted at  $p=.05$  level. Data will be analyzed using descriptives (means, medians, standard deviations of scores), independent t-tests, correlation coefficients and analysis of variance. In Aim 1, ANOVA will be used to assess differences between the three treatment groups on the YFAS to determined changes in MI confidence, importance and readiness to change scores as well as ASA24-2016® dietary recall and biometric measures. Correlational analysis will be used to explore the relationships between ASA24-2016® dietary recall and biometric measures. In Aim 2 independent t-test will be used to determine if the positive and negative YFAS groups differ across treatment responses.

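### If 40 is the randomised total, 50% attrition leaves 20 completers (7.9% of 252), short of the 10% rule; if 80 are randomised, the rule holds but the enrolment figure of 40 is wrong

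*Combined protocol and SAP*

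**What the plan says.** All of the following is in the combined protocol and SAP.

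- **Fully powered size.** Under Contribution to Science, in the sample-size paragraph, with f = 0.25, alpha 0.05 and power 0.95, the "a priori F test, analysis of variance, omnibus, one-way model gives a projected sample size of 252".
- **Pilot size.** The same paragraph calls the pilot underpowered for hypothesis testing and says "a sample of 40 eligible patients will be enrolled (10 in each group").
- **Justification.** The next sentence reads "This meets the pilot study guideline of at least 10% of a fully powered trial and remains realistic in terms of time and cost", and after a literature citation it ends "while allowing for 50% attrition". No number of completers is given.
- **What the 40 refers to.** Two sentences on, the screening calculation expects 25% of 160 consented people to be positive for food addiction (FA), and uses 40 as the number of FA-positive people to be reached.
- **Randomisation target.** Under Proposed methods/approach, in the paragraph on initial screening, participants are randomised 1:1:1:1 within each phenotype, and assignment continues until there are 10 in every combination of phenotype and treatment.

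**The concern.** With power disclaimed, the 10% rule and its attrition allowance are the only quantitative support for the pilot's size; the other reason in the same sentence is feasibility in time and cost. Allowing for attrition ordinarily means that the target still holds once the losses have occurred. Someone approving or funding the study would conclude that half the patients can be lost and the benchmark still met.

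On the three figures in that paragraph (252, 40, 50%) that conclusion does not follow. The expected number of completers, which determines how precisely effect sizes can be estimated, is never stated. It differs by a factor of two according to whether the randomised total is 40 or 80.

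**Working it through.** **Inputs.** From the sample-size paragraph: full-trial N = 252, f = 0.25, alpha = 0.05, power = 0.95, pilot enrolment 40, guideline 10%, attrition 50%. From the randomisation paragraph: 10 per cell, 2 phenotypes, 4 treatments.

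**1. Reproduce 252.** Power of the one-way omnibus F test uses the noncentral F distribution with noncentrality f² × N and k − 1 and N − k degrees of freedom.
- k = 3: the smallest N is 251, or 252 in equal groups; power at 252 is 0.951. This matches the plan.
- k = 4: the smallest N is 279, or 280 in equal groups; power at 252 is 0.926.

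The stated figure therefore reproduces for three groups, although the text says "The design is a stratified four-group design with a pre and post measurement". That is a separate matter. The check below uses the plan's 252 and gives 280 as a sensitivity.

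**2. What the rule requires.** 0.10 × 252 = 25.2, so 26 whole patients (25/252 = 9.9% falls short).

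**3. If 40 are randomised.**
- At enrolment: 40/252 = 15.9%. Rule met.
- After 50% attrition: 40 × (1 − 0.50) = 20; 20/252 = 7.9%. Rule not met. 20/4 = 5 completers per arm.
- Largest loss that keeps the rule: 40 − 26 = 14; 14/40 = 35%. The unrounded limit, 1 − 25.2/40 = 37%, is not attainable, because losing 15 leaves 25.
- Enrolment at which the sentence would hold as worded: 25.2/(1 − 0.50) = 50.4, so 51, or 52 in four equal groups of 13.

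**4. If 80 are randomised.**
- 2 × 4 × 10 = 80, or 40 per phenotype.
- After 50% attrition: 80 × 0.50 = 40; 40/252 = 15.9%. Rule met. 40/4 = 10 completers per arm and 40/8 = 5 per cell.
- The ceiling of 160 consented is compatible with this: 160 × 0.25 = 40 FA-positive and 160 − 40 = 120 FA-negative, of whom 40 would be needed.

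**5. Sensitivity to 280.**

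| Randomised | Left after 50% attrition | % of 252 | % of 280 | 10% met |
|---|---|---|---|---|
| 40 | 20 | 7.9 | 7.1 | no |
| 80 | 40 | 15.9 | 14.3 | yes |

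The answer does not depend on which full-trial N is used. It depends on whether 40 or 80 are randomised.

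**The case against.** **The rule may be meant at enrolment.** The text says 40 are enrolled and that this meets the guideline; 40/252 = 15.9%, so that is true. The attrition clause follows the remark on time and cost and could be attached to that. Whether the guideline counts enrolled or completing patients depends on a cited source that was not available for this review. This stands as a reason to make the conclusion conditional. It does not rescue the sentence, because on this reading the attrition clause has no content.

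**The true total may be 80.** The screening calculation ties the 40 to FA-positive people, and the randomisation paragraph implies 80. On that reading the 10% claim is correct. This also stands, and it is why a reader who infers that the claim is simply false goes too far. The error then moves to the enrolment statement, so the paragraph still needs correcting.

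**It is only a pilot.** The plan says that it is underpowered and will concentrate on description, effect-size estimation and hypothesis generation. No power claim rests on the 10% rule. This stands and limits the weight of the point. A reader might infer that the pilot is too small or must enrol more; nothing here shows that.

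**A tempting explanation of the 40.** Inflating 25.2 by 1 + 0.5 gives 37.8, close to 40, whereas dividing by 1 − 0.5 gives 50.4. One might infer that the wrong inflation formula was used. The documents do not show how 40 was derived, so this remains conjecture.

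**Conclusion.** The point holds conditionally. If 40 is the total randomised and the 10% rule is to hold after the stated attrition, the plan's statement fails: 20 completers, 7.9% of 252, against 26 needed, with a tolerable attrition of 35% rather than 50%. If 80 are randomised, the rule is met with 40 completers (15.9%), and it is the enrolment figure of 40 that is wrong. The documents support both totals and do not settle which is meant.

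The conclusion rests on the plan's own wording of the guideline, on its figure of 252, and on 50% being loss from the randomised total. The arithmetic is certain; which total is intended is not. The effect is confined to the justification of the pilot's size and the expected number of completers. It does not touch safety, the conduct of the trial or the choice of analysis.

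**What to change.** Reconcile the enrolment of 40 in the sample-size paragraph with the 80 implied by the randomisation paragraph, then restate the sentence to match. Suggested wording:

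- (a) If 80: *80 randomised (40 per phenotype); after 50% attrition about 40 completers, about 16% of 252.* Correct the enrolment statement to 80.
- (b) If 40: *40 randomised, 16% of 252 at enrolment; after 50% attrition about 20 completers (8%, about 5 per arm), below the 10% guideline, which is met only if attrition is at most 35%.* Correct the per-cell target in the randomisation paragraph.

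If the full-trial N is recalculated for four groups (280 by the calculation above), update the percentages: 14.3% under (a); under (b), 14.3% at enrolment, 7.1% after attrition, and a limit of 30% (28 of 40 must remain, so 12 may be lost).

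The cost is the rewording of one or two sentences, with no change in design or analysis and no call for more patients. Under (b) the stated justification becomes less favourable.

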#### Proposed methods/approach

Investigators propose assessing obese clients with the YFAS as part of their intake once they are referred to the Healthy Behaviors Clinic by Regional West physicians/practitioners. A nurse researcher with expertise in MI and a nurse practitioner will perform intake assessments, obtain consent and randomly assign participants in each phenotype (positive or negative for FA) to one of three treatment groups (usual care, individual MI alone, and individual MI with pharmacotherapy). Interventions will occur over 6 months. A clinical psychologist with expertise in the YFAS (University of Michigan) will serve as a consultant on this project and a registered dietitian (University of Nebraska Lincoln) will serve as a co-investigator.

Investigators expect that MI and MI+P and P will be more effective in improving outcome measures than IC. We also expect that response to the treatments will differ between the two obesity phenotypes (those testing positive and those testing negative for FA).

To determine if MI alone or MI+P or P is effective in treating obese patients with and without FA (based on the YFAS) as determined by :

- Higher MI confidence, importance and readiness to change scores
- Reduced intake of foods that are highly processed and high in fat and sugar (HPFS) and increased intake of complex carbohydrate foods(fresh fruits, vegetables, whole grains) and minimally processed proteins (nuts, fresh meats) (ASA24-2016® dietary recall)
- Improved biometric measures (BMI, body composition, waist circumference, and blood pressure)

-To determine whether the two obesity phenotypes (with and without FA) differ in their response to the four treatments.

**Initial Screening for Eligibility (Suicidal Ideation, Pregnancy test (urine test), Lactation, Recruitment):**  
Participants will be recruited from obese patients referred to the Healthy Behaviors Clinic by Regional West Physicians. Nurse researchers who work at the Healthy Behaviors Clinic will inform potential participants about the study and, if they agree to participate, will consent them.

Both treatment groups, Those who test positive for and those who test negative for FA (food addiction) will be assigned to one of four treatment arms, IC, MI, MI+P and P. All will receive dietary and exercise information. After consenting, each participant will be administered the YFAS to determine their obesity phenotype (positive or negative for FA). Participants within each phenotype will be randomly assigned to one of the intervention (MI or MI+P, or P) or the IC information control (diet and physical activity instruction, which will be no less than current standard of care) treatment groups using a randomization schedule (assignments in numbered, sealed, opaque envelopes; one set for each phenotype) 1:1:1:1 ratio, provided by our statistician, [name]. Phenotype assessment and treatment assignment will continue until the sample size (n=10) is met for each phenotype-treatment group category. Those in the control group will be seen at the same time periods as each treatment group to maintain their interaction time with the clinic. They will receive diet and exercise instruction at each time point.

**Intervention Conditions (MI, MI+P):** MI is theorized to decrease a patient's ambivalence and increase his/her perceived behavioral control (self-efficacy) for limiting HPFS and increasing CC intake by emphasizing personal choice and control in decision-making and by affirming the patient's self-management ability. Interventionist nurses will deliver MI sessions following data collection at baseline, 1, 2, 3, and 4 weeks and 2, 3, 4, 5, and 6 months to promote sustained behavioral change. A written MI algorithm will be used to ensure uniform implementation of the intervention.

MI will be operationalized by the nurse asking the patient about his/her knowledge, limiting HPFS/increasing CC and natural fat intake, defining FA, and explaining why it is important to limit their HPFS/increase their CC and natural fat intake. The nurse will ask the patient to rate the importance of limiting HPFS/increasing CC and natural fat intake (scale of 1-10) and their confidence in their ability to do so (scale of 1-10). The nurse will focus on the lower score and ask the patient why they chose that score and what they thought it would take to increase the number. If the patient rates the importance of understanding of limiting HPFS/increasing CC and natural fat intake low, the nurse will provide information on the benefits of limiting HPFS/increasing CC and natural fat intake to reduce their risk of obesity, diabetes, heart disease, and numerous other co-morbidities associated with overweight. If the patient rates their confidence in their ability to limit HPFS/increase CC and natural fat intake as low, the nurse will provide the patient with strategies to decrease barriers and increase confidence, such as a list of healthy snack food choices, stepped changes (3 sodas per day to 2 sodas and 1 water per day, etc.), and having the patient choose healthy foods at the store. The same questions will be asked at each time point.

Nurse responses will be tailored to the specific motivational issues of each individual patient at each time point. During each session, the nurse will document the patients responses to the MI algorithm (levels of confidence, importance, and readiness to change), their perceived barriers and concerns, and suggestions to address them/setting achievable goals. The MI documentation form will ensure that all nurses collect the same data and provides a record that the nurses can reference during their sessions to help them adjust each MI session to the patients' individual needs. If a patient reveals a new barrier that is not included in the training materials, the nurses will meet with team members to discuss the new barrier and strategies to address it will be shared with all interventionists.

In the group with pharmacotherapy added to the MI, the naltrexone-bupropion (Contrave) protocol will be added to the patients intervention. Dosing protocols will be followed for treatment of obesity: Orally, 1 tablet (90mg/8mg) initially week 1; increase by 1 tablet/day each subsequent week until daily maintenance dose of 2 tablets twice daily (360 mg bupropion/32 mg naltrexone) is achieved at the start of week 4. Use will be discontinued at month 4 if no clinical response is observed. This drug (Contrave) is to be taken with a high fat meal.

In the pharmacotherapy group alone, dosing protocols will be followed for treatment of obesity: Orally, 1 tablet (90mg/8mg) initially week 1; increase by 1 tablet/day each subsequent week until daily maintenance dose of 2 tablets twice daily (360 mg bupropion/32 mg naltrexone) is achieved at the start of week 4. Use will be discontinued at month 4 if no clinical response is observed. This drug (Contrave) is to be taken with a high fat meal.

The IC control group will receive diet and physical activity information to encourage them to adopt healthier eating (limit HPFS/increase CC intake) and physical activity behaviors. IC information sessions will occur at the same time points as the intervention sessions (baseline, 1, 2,3, and 4 weeks and 2, 3, 4, 5, and 6 months) and will be similar in length. The PI and co-PIs will develop information packets for each session, (self-management, avoiding highly processed LNSC foods, low intensity physical activity, avoiding highly processed fatty foods, medium intensity physical activity, avoiding LNSC beverages, importance of water as a beverage to hydrate and reduce cravings, avoiding high fat beverages, high intensity physical activity, importance of CC intake).

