Waist circumference: We will use the average of 2 measurements (cm) performed with the patient standing erect with their arms at their sides. Waist circumference will be measured at the uppermost lateral border of the right ilium at the end of normal expiration using an inelastic tape measure positioned around the trunk parallel to the floor. This measure is included because it is a better indicator of body fat and, therefore, health risk than

BMI: In addition, results of a recent study in this population demonstrated that waist circumference has potential as a means of identifying patients with or at risk for obesity and hypertension.

Blood Pressure: We will use the average of 2 blood pressure measurements performed using an Omron HEM- 907 automatic blood pressure monitor. The measurements will be performed while the patient is quiet and still using the appropriate sized cuff placed snugly around the upper arm approximately 2 to 3 cm above the antecubital fossa with the mark on the cuff aligned with the artery.

Determinants of Change Measures: MI Algorithm Questions: These reflect the PCBT determinants of behavior change (the patients perceptions toward limiting HPFS/increasing CC intake). They assess patient attitudes/beliefs (importance score), perceived norms (perceived barriers), and perceived behavioral control/self-efficacy (confidence score). These measures will be recorded by the interventionist nurses during each MI session for their assigned patients.

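### The only baseline importance, confidence and readiness ratings are taken inside the first MI session, after randomisation and probably after some intervention content, so change from baseline may understate the within-arm MI effect

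*Combined protocol and SAP*

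**What the plan says.** All references are to the combined protocol and SAP.

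- **Outcome.** Proposed methods/approach lists "Higher MI confidence, importance and readiness to change scores" first among the signs that a treatment works. Statistical Methods to Analyze Data applies ANOVA to changes in these scores. The sample-size justification describes a pre and post design.
- **Timing of sessions.** The Intervention Conditions (MI, MI+P) text, under Initial Screening for Eligibility, states: "Interventionist nurses will deliver MI sessions following data collection at baseline, 1, 2, 3, and 4 weeks and 2, 3, 4, 5, and 6 months". There is thus an MI session at baseline.
- **Where the ratings are recorded.** Determinants of Change Measures, under Data Collection, says of the importance and confidence scores: "These measures will be recorded by the interventionist nurses during each MI session for their assigned patients". The Intervention Conditions text likewise has the nurse document confidence, importance and readiness during each session.
- **Content of the session.** The nurse asks about knowledge, defines food addiction and explains the importance of the dietary change. The request for ratings on a 1 to 10 scale follows in the next sentence: "explaining why it is important to limit their HPFS/increase their CC and natural fat intake. The nurse will ask the patient to rate". If the importance rating is low, "the nurse will provide information on the benefits of limiting HPFS/increasing CC and natural fat intake to reduce their risk of obesity". Strategies follow a low confidence rating in the same way.
- **Repetition.** "The same questions will be asked at each time point".

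**The concern.** A baseline value should be taken before the intervention can affect it. Here the baseline rating is given to the treating nurse, within the first session of the treatment under study, and apparently just after the patient has been told why the behaviour is important.

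The explanation is aimed at the construct being rated. The background text on motivational interviewing says that sharing information on benefits addresses attitudes and beliefs. Determinants of Change Measures says that the importance score assesses attitudes and beliefs. Whatever the explanation adds for good is then counted in the starting value and not in the change.

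The pilot's stated products are descriptive statistics and effect-size estimates, so a displaced baseline feeds into a figure the study is meant to deliver. Dietary recall and biometric measures are not implicated: the plan places data collection ahead of each session.

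**Working it through.** The documents give no figure for these ratings, so there is nothing of theirs to reproduce. The check has two parts.

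**1. Reading the timing together**

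1. Participants consent, complete the YFAS and are then randomised by envelope (Initial Screening for Eligibility).
2. MI sessions belong to the arms assigned MI. A patient in a baseline MI session has therefore already been randomised.
3. The ratings are recorded during the session, and no other rating is described. The only pre value is therefore post-randomisation. This holds whatever the order within the session.
4. Within the session, the explanation is listed before the rating. The text contains no word such as then, before or after, so this order is an inference from sentence order.
5. The information on benefits given after a low importance rating, and the strategies given after a low confidence rating, come after the rating they respond to. They cannot affect the baseline score.

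**2. What this does to a change from baseline**

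Notation (all values assumed):
- B: rating the patient would give before the first session.
- T: true change in the pre-session rating by month 6.
- p: part of the opening explanation's effect that lasts. It is included in T.
- t0 and t6: transient lifts from the explanation at baseline and at month 6.

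Recorded baseline = B + p + t0.
Recorded month 6 = B + T + t6.
Recorded change = T − p + (t6 − t0).

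If the transient lift is the same at both visits, t6 − t0 = 0 and the recorded change is T − p. The share missed is p / T:

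| T | p | Recorded change | Share missed |
|---|---|---|---|
| 2 | 0 | 2.0 | 0% |
| 2 | 0.5 | 1.5 | 25% |
| 2 | 1.0 | 1.0 | 50% |
| 2 | 1.5 | 0.5 | 75% |
| 3 | 0.5 | 2.5 | 17% |
| 3 | 1.0 | 2.0 | 33% |
| 3 | 1.5 | 1.5 | 50% |

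A single example shows why the recorded data cannot settle the matter. Suppose the rating is 6 before the first session, 8 after the explanation, and 8 in the month 6 session. The recorded change is 8 − 8 = 0.
- If the 2-point lift lasted, the pre-session rating at month 6 is 8, the true change is 8 − 6 = 2, and all of it is missed.
- If the lift is transient and recurs, the pre-session rating at month 6 is 6, the true change is 0, and the recorded 0 is correct.

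In both cases the room left on the scale falls from 10 − 6 = 4 points to 10 − 8 = 2.

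**The case against.** Several points against the concern stand.

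- **The order is not a stated rule.** The sentence on how MI is carried out could be a list of components that later sentences expand. The written MI algorithm and the documentation form would fix the order, and neither is reproduced. This limits the claim about explanation before rating. It does not affect the finding that the rating is in-session and post-randomisation.
- **Sessions follow data collection.** That general statement leaves room for a pre-session rating. The two places that deal specifically with these ratings, however, put them inside the session.
- **No baseline or change score is defined.** The statistical section speaks only of changes. That is correct, and it leaves the in-session rating as the only candidate for the pre value.
- **This is a pilot**, declared underpowered and descriptive. That lowers the stakes, although effect-size estimation is one of its stated aims.

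Three stronger readings are tempting, and the documents support none of them.

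- A reader might infer that the baseline already holds the effect of the whole first session. At most it holds the effect of a general explanation, because the score-driven content comes after the rating.
- A reader might infer that the MI arms are compared with IC and P from unequal baselines. Ratings are described only in MI sessions, so that contrast is hypothetical. All arms also receive diet and exercise information, so an unprimed baseline in IC and P could not be assumed.
- A reader might attach a definite number of points to the bias. The documents supply nothing to estimate it from.

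**Conclusion.** The point holds in a limited form. The only baseline value for the first-listed outcome is recorded by the treating nurse, after randomisation, inside the first MI session. In the order written, the importance rating also follows an explanation of why the behaviour matters. The explanation bears most directly on importance; for confidence and readiness the firmer problem is the in-session, post-randomisation timing.

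Any lasting gain from the explanation is lost from the change from baseline, so the within-arm MI effect would tend to be understated. The size is unknown: zero if nothing lasts, and 17% to 75% of the true change in the non-zero cases tabulated. The direction rests on three assumptions:

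- the session runs in the order described;
- some of the gain from the explanation persists;
- the transient lift is similar at baseline and at month 6.

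This is worth correcting because the remedy is cheap. It does not undermine the study's other outcomes.

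**What to change.** - Collect importance, confidence and readiness on a short patient-completed form in the data-collection step that already precedes each session.
- At baseline, have the form completed before the randomisation envelope is opened, for example alongside the YFAS. Every participant then has a baseline value, whatever the arm.
- State in Statistical Methods to Analyze Data that these pre-session ratings are the outcome and that change is measured from the pre-randomisation form.
- Keep the ratings asked within the session as counselling tools only.

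The cost is protocol wording and one short form, with no extra visit. Patients answer the same few questions twice on session days, and having just answered the form may slightly anchor the in-session ratings that guide counselling. That is a small price for a baseline free of intervention content.
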